10. Creatine Kinase: Scheduled CK tests are only drawn at screening, baseline, and, annually thereafter. If a subject complains of muscle discomfort at a visit, a CK level should be drawn. If at any time a CK level is > 5X the upper limit of normal (ULN), an unscheduled visit should be scheduled for a repeat CK, within 48 hours if possible, with CK fractionation for isozymes (to assess CK-MM and CK-MB) and urine dipstick. Unscheduled measurements of CK do not require fasting. See [Section 7.2.5](#), [Section 7.6](#) and [Appendix 7](#).  
Prior to obtaining blood for a CK assessment, investigators should enquire about recent intramuscular injections, heavy exercise, or recent musculoskeletal trauma, and defer CK testing until the next visit or repeat testing at an unscheduled visit, no less than 7 days after the IM injection or musculoskeletal trauma, so as to avoid spuriously elevated values.
11. ADA/PK/PCSK9 sampling: Anti-drug antibody (ADA), bococizumab drug, and PCSK9 blood samples should be collected in all subjects, at the baseline and designated visits as described in [Section 6](#). For Visit 3, only a PCSK9 sample is needed. No PK or ADA sample is needed at Visit 3. After randomization, if lipid sampling has been postponed to an unscheduled visit, the corresponding ADA/PK/PCSK9 samples should be postponed as well, and collected at the same time as the rescheduled lipid sample collection. ADA, PK, and PCSK9 samples will be collected at EDC/EOS visits.
12. Hematology: Complete blood count (CBC) with white blood cell (WBC) and red blood cell (RBC) counts, hemoglobin, hematocrit, WBC differential and platelet count. All hematology studies are to be performed by central laboratory.
13. Urinalysis: Dipstick urinalysis will be performed by study site, locally. Details describing what is evaluated in the urinalysis are described in [Section 7.2.1.2](#), [Table 2](#). At the screening visit a central lab urine albumin/creatinine ratio assessment may be evaluated, in subjects who have had a cardiovascular event more than 5 years prior to screening and in subjects without a prior qualifying cardiovascular event.

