- **IRT interaction:** At the time of the visit, the visit will be registered in the IRT which will trigger an allocation of investigational product for the subject, except at the EDC or EOS visit. At the EDC or EOS visit, the EDC or EOS status will be registered.
- **Investigational product:** Dispense investigational product based on IRT randomization code (except for EDC or EOS visit). If there is dosing during the visit, subjects will be observed, at the visit, during the injection of investigational product, either by self-injection, or as performed by a care giver, after all other procedures have been completed. Except for EDC or EOS visit, subjects will be provided with investigational product kits to bring home with them and will be reminded about storage conditions.
- **Compliance check:** The subject's compliance with investigational product administration, as described in [Section 5.3](#), will be assessed. Subjects will be instructed to bring any used and unused syringe cartons to each visit. Used syringes

will be returned to the study center in a biohazard container, when it is full, to receive a new container, and when directed by the study site, as described in [Section 5.3](#). Compliance with lifestyle guidelines should also be reviewed ([Section 4.4](#)) and recorded in the CRF.

- **Contraception check:** A contraception check should be made for male and female subjects, who, with their partner, are of childbearing potential ([Section 4.4.2](#)).

The following laboratory tests will be collected:

- Blood for fasting lipid profile:

Lipid level tests should be scheduled no sooner than 10 days after the subject's prior dose, even if this requires an unscheduled visit;

If a subject has a visit that is scheduled less than 10 days after the last dose, the visit procedures may take place, but lipid testing should be postponed and performed at the earliest possible time, at an unscheduled visit, no sooner than 10 days after the subject's last dose;

A lipid profile will not be collected at EDC/EOS visits;

- Special lipid and efficacy studies as described in [Section 7.1.2.2](#), at Week 52, Visit 11;
- Biospecimens as described in [Section 7.5](#), at Week 52, Visit 11;
- Chemistry group (including LFTs and CK level);
- Hematology;
- Urinalysis;
- HbA1c for all subjects at Visit 11 and EDC and/or EOS;
- Blood specimens acquired for ADA, bococizumab level, and PCSK9 level in all subjects at Visits 14, 17, 20, and EDC or EOS;

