8.2.3. Analysis of Safety Data

Safety will be assessed through adverse events (including Type 1 and 3 hypersensitivity reactions and injection site adverse events), serious adverse events, vital signs, examination results (physical and neurologic examinations and cognitive testing), 12-lead ECG recordings, and safety laboratory tests including hematology, blood chemistry studies (including liver function tests and creatine kinase tests), urinalysis studies, and ADA assessments. The Safety Analysis Set (SAS) includes all subjects who have received at least one dose of randomized study medication and will be used for all safety analyses, unless otherwise specified. All summaries of safety data will be descriptive only, unless indicated otherwise.

For summaries by visit, observations will be assigned to visits according to the analysis windows in [Table 4](#).

Adverse Events

The Medical Dictionary for Regulatory Activities (MedDRA) will be used to classify all AEs with respect to system organ class and preferred term. AEs, AEs leading to discontinuation from treatment, and SAEs after the first dose of study medication will be tabulated by treatment group. AEs after the first dose of study medication will be summarized without any requirement that the intensity increase after the first dose of study medication. Summaries will also be provided by severity. Summaries by the relationship to study therapy will be provided for AEs and SAEs only.

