Observed values and changes from baseline in systolic BP, diastolic BP, PR, and weight will be tabulated by visit as continuous endpoints according to sponsor standards. Height, waist circumference, and temperature will be listed.

Anti-drug antibody (ADA) and neutralizing antibody (nAb)

The number of samples analyzed for ADA and nAb will be summarized.

ADA and nAb status will be summarized as categorical endpoints by visit and overall at the subject level. The numbers and percentages of ADA positive and nAb positive subjects classified according to timing of first result with respect to last dose of bococizumab (on treatment/off treatment) and characterization of ADA and nAb response (treatment induced/treatment boosted/indeterminate) using the definitions in [Section 6.2](#) will be presented.

In addition, the summary of nAb will be repeated with two different denominators: number of non-missing ADA samples and number of ADA positive subjects.

Antibody titers for ADA positive subjects and nAb positive subjects will be summarized by visit as continuous endpoints. Boxplots of ADA titer and nAb titer over time will be presented.

Time to first positive ADA result and time to first positive nAb result will be summarized as continuous endpoints in the subgroups listed [Section 5.4.2.5](#).

Clinical laboratory measurements

Observed values and changes from baseline in hematology, blood chemistry, and quantitative urinalysis parameters will be tabulated by visit as continuous endpoints according to sponsor standards. Mean changes from baseline will be plotted longitudinally for selected laboratory parameters including creatine kinase, hemoglobin, HbA1c and glucose, according to sponsor standards. Qualitative urinalysis parameters will be listed.

Observed value and change from baseline in HbA1c will be tabulated by visit as continuous endpoints for the subgroup identified in [Section 5.4.2.3](#).

Laboratory shift tables for hemoglobin, CK, glucose, and HbA1c will summarize shifts from baseline status (below lower limit of normal, normal, above upper limit of normal) to post-baseline status at each scheduled measurement. Shifts from baseline to the smallest post-baseline and largest post-baseline measurement will also be tabulated. These shift tables will also be done for the subgroups identified in [Section 5.4.2.3](#).

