10. APPENDICES

Appendix 1. DATA DERIVATION DETAILS

Appendix 1.1. Definition and Use of Analysis Windows in Reporting

The MMRM models for circulating biomarkers and cognitive assessments, and summaries of safety variables (including depression assessments) will require the assignment of observations to scheduled visits, i.e., analysis windows. Safety summaries and analyses will use a different set of windows than summaries and analyses of circulating biomarkers. For safety analyses, the windows will be based on the subject's date of first dose on randomized study medication; the first day of dosing is Day 1. For other summaries and analyses, the day of randomization is Day 1. For both safety and efficacy analyses, if two or more measurements fall in an analysis window, the measurement closest to the target day will be used.

The following table contains the analysis windows for circulating biomarkers and outcomes research variables.

Table 3. Analysis Windows for Circulating Biomarkers and PK/PD

Visit Label	Target Day	Randomization Days*
Visit 6: Week 4 (Month 1)	29	19-39
Visit 7: Week 8 (Month 2)	57	47-67
Visit 8: Week 14 (Month 3)	99	89-109
Visit 9: Week 26 (Month 6)	183	153-213
Visit 10: Week 40 (Month 9)	281	251-311
Visit 11: Week 52 (Month 12)	365	335-395
Visit 12: Week 70 (Month 16)	491	461-521
Visit 13: Week 86 (Month 20)	603	573-633
Visit 14: Week 104 (Month 24)	729	699-759
Visit 15: Week 122 (Month 28)	855	825-885
Visit 16: Week 140 (Month 32)	[contact]
Visit 17: Week 156 (Month 36)	1093	1063-1123
Visit 18: Week 174 (Month 40)	1219	1189-1249
Visit 19: Week 192 (Month 44)	1345	1315-1375
Visit 20: Week 208 (Month 48)	1457	1427-1487

*Randomization days = measurement date – Day 1 (randomization date) + 1

The safety windows will touch, so that all post-baseline safety observations will fall in a window. The following table contains the windows for safety analyses.

Table 4. Analysis Windows for Safety Including Cognitive Assessments

Visit Label	Target Day	Study Days*
Visit 6: Week 4 (Month 1)	29	2-42
Visit 7: Week 8 (Month 2)	57	43-77
Visit 8: Week 14 (Month 3)	99	78-140
Visit 9: Week 26 (Month 6)	183	141-231
Visit 10: Week 40 (Month 9)	281	232-322
Visit 11: Week 52 (Month 12)	365	323-427
Visit 12: Week 70 (Month 16)	491	428-546
Visit 13: Week 86 (Month 20)	603	547-665
Visit 14: Week 104 (Month 24)	729	666-791
Visit 15: Week 122 (Month 28)	855	792-917
Visit 16: Week 140 (Month 32)	[contact]
Visit 17: Week 156 (Month 36)	1093	1037-1155

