6. Cognitive Testing: Cognitive testing will be performed in a subset of designated North American (U.S. and Canada) study sites, at baseline (Visit 5), annually, and EDC or EOS visits only as described in Section 7.2.3.4.
7. ECG: Regularly scheduled ECGs are to be recorded locally, anonymized, saved in the study file, and a copy of the ECG should be sent to the study central ECG file for storage. If a subject experiences a nonfatal adjudicated and confirmed CV event after randomization, a new baseline ECG should be performed following the event. It may be done at a regularly scheduled visit if the visit is to occur within that time frame. If not, a new ECG should be performed at an unscheduled study visit.
8. Chemistry Group: At indicated visits only: sodium, potassium, chloride, bicarbonate, creatinine, blood urea nitrogen (BUN; serum urea), glucose. All chemistry studies are to be performed by central laboratory.
9. Liver function tests: Liver function tests, including ALT, AST, alkaline phosphatase, and total and direct bilirubin, should be performed at the designated visits. Unscheduled visits for reassessing liver function test abnormalities may be required (Section 8.6.2. and Appendix 8) and do not require fasting.
10. Creatine Kinase: Scheduled CK tests are only drawn at screening, baseline, and, annually thereafter. If a subject complains of muscle discomfort at a visit, a CK level should be drawn. If at any time a CK level is > 5X the upper limit of normal (ULN), an unscheduled visit should be scheduled for a repeat CK, within 48 hours if possible, with CK fractionation for isozymes (to assess CK-MM and CK-MB) and urine dipstick. Unscheduled measurements of CK do not require fasting. See Section 7.2.5, Section 7.6. and Appendix 7.
Prior to obtaining blood for a CK assessment, investigators should enquire about recent intramuscular injections, heavy exercise, or recent musculoskeletal trauma, and defer CK testing until the next visit or repeat testing at an unscheduled visit, no less than 7 days after the IM injection or musculoskeletal trauma, so as to avoid spuriously elevated values.

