28. Early discontinuation (EDC) procedures should be done upon the permanent early discontinuation of double-blind investigational product. Study sites must contact the study retention team, or delegate, or EDC retention hotline (by telephone or email) for all potential or actual EDC subjects. Subjects should continue to have visits (either in person or via phone visit) with study personnel according to the study schedule until study completion. Subjects who continue in the study, after EDC, should also complete EOS procedures, at the time of study completion.
29. The EOS visit will be announced to study sites, when the Sponsor estimates that criteria for stopping the study in Section 3 have been satisfied. EOS visits should be scheduled as soon as possible after that announcement. The EOS visit should occur no sooner than 14 days after the last dose of investigational product was administered for subjects taking IP. The safety follow-up period is 40 days after the last dose of IP was administered. If their EOS visit has occurred less than 40 days after the last dose of IP was administered, subjects should be contacted by telephone to determine if any serious adverse events have occurred. All EOS procedures should be done for all randomized subjects when the study is completed, whether or not the subject is taking double-blind investigational product.

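### CK is scheduled in only 4 of the 15 safety windows, so mean CK change tabulated and plotted across all windows is not comparable from visit to visit

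*SAP*

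**What the plan says.** **When CK is drawn.** Protocol Schedule of Activities, footnote 10: "Scheduled CK tests are only drawn at screening, baseline, and, annually thereafter". The flowchart and Protocol 6.4.4 add CK at EDC and EOS. The same footnote adds triggered draws: "If a subject complains of muscle discomfort at a visit, a CK level should be drawn", and after a value above 5x ULN "an unscheduled visit should be scheduled for a repeat CK, within 48 hours if possible". It also tells sites to defer CK after an intramuscular injection, heavy exercise or muscle trauma. Protocol 8.6.2 includes CK in the work-up of potential liver injury. On EOS, footnote 29 says: "All EOS procedures should be done for all randomized subjects when the study is completed", whether or not the subject is on study drug.

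**How CK is summarised.** SAP 8.2.3 tabulates observed values and changes in chemistry by visit. For the figure it says "Mean changes from baseline will be plotted longitudinally for selected laboratory parameters including creatine kinase, hemoglobin, HbA1c and glucose", according to sponsor standards. On visit assignment it says "For summaries by visit, observations will be assigned to visits according to the analysis windows in" Table 4. SAP Appendix 1.1 says of that table: "The safety windows will touch, so that all post-baseline safety observations will fall in a window". Where a subject has several values in one window, the one nearest the target day is used. SAP 6.2 keeps every non-missing measurement after the first dose, on or off drug. The CK shift tables in 8.2.3, in contrast, are tied to scheduled measurements, with separate shifts to the smallest and largest post-baseline value.

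**The concern.** A longitudinal plot of means invites the reader to see one population followed over time. For CK, the population changes from point to point. At the annual visits every subject still attending is due a routine draw. At the other visits a value exists only because the subject had muscle symptoms, had a high result, had a liver work-up, had a routine test postponed, stopped treatment, or reached the end of the study. A rise or fall between adjacent points can then reflect who was sampled, not any change in CK.

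CK has its own myopathy monitoring rules in Protocol 7.2.5 and is one of four parameters named for the plot. The mean-change plot is the only CK figure that SAP 8.2.3 now specifies. A misleading time course could suggest a CK signal that is absent, or make a real one hard to read.

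**Working it through.** The plan states no figure for this point, so there is none to reproduce. The check is a count, then an illustration of what the off-schedule windows would contain.

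**1. Count of windows.** Table 4 has 15 windows (Visits 6 to 20). The Visit 16 row is partly lost in the text available; its neighbours imply Days 918 to 1036. Scheduled annual CK falls at Visits 11, 14, 17 and 20, which is 4 windows. Without a scheduled annual CK: 15 − 4 = 11, and 11/15 = 73%. These are Weeks 4, 8, 14, 26, 40, 70, 86, 122, 140, 174 and 192.

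**2. Do annual draws made on time land in their own windows?** Target day = 7 × week + 1, plus or minus the protocol visit window.

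| Visit | Permitted days | Table 4 window |
|---|---|---|
| Week 52 (±3) | 362–368 | 323–427 |
| Week 104 (±14) | 715–743 | 666–791 |
| Week 156 (±14) | 1079–1107 | 1037–1155 |
| Week 208 (±14) | 1443–1471 | 1401 onward |

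All four do. On-time annual draws therefore never reach the other 11 windows, and the nearest-to-target rule has no annual value there to prefer over a triggered one.

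**3. Where EOS values go.** Table 4 has no EDC or EOS row. Entry was staggered and the programme stopped on 01 November 2016, so EOS values enter whichever window matches time since first dose.

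**4. Illustration of the mix.** From Protocol 9.1: 17,000 subjects, 3.1 years of accrual, half in the last ten months. Assumed, because the documents do not give them: EOS 15 to 180 days after the last randomization; symptom-triggered CK at 2% or 5% per year, paired with EDC at 5% or 10% per year; every subject has an EOS draw. Repeats, liver work-ups and deferred draws are left out. Share triggered, p = triggered / (triggered + EDC + EOS).

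| EOS after last randomization | Week 4: EOS values, p | Week 8: EOS values, p | Week 14: EOS values, p |
|---|---|---|---|
| 15 days | 735, 4–9% | 956, 3–6% | 1,707, 3–6% |
| 60 days | 0, 29–33% | 447, 6–12% | 1,731, 3–6% |
| 120 days | 0, 29–33% | 0, 29–33% | 507, 8–15% |
| 180 days | 0, 29–33% | 0, 29–33% | 0, 29–33% |

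The 29–33% follows directly from the assumed rates: 2/(2 + 5) = 0.29 and 5/(5 + 10) = 0.33. In every scenario the Week 26 and 40 windows hold about 1,400 to 2,600 EOS values, with p of 2–10%. In the off-schedule windows from Week 70 on, p is about 8% or less, and the last windows are nearly empty.

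**5. Effect on the mean.** If triggered values exceed the others by Δ in mean change, the window mean shifts by p × Δ. At Weeks 26 and 40 that is 0.02Δ to 0.10Δ. In an early window without EOS values it is 0.29Δ to 0.33Δ. The documents give no Δ, so this cannot be turned into CK units.

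**The case against.** A reader might infer that most plotted visits contain only symptomatic subjects, repeats of high values and discontinuers, and that the plot will therefore show a false early CK rise. The documents do not support that.

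- EOS draws are due in all randomized subjects and spread across the windows. In the illustration they dominate from Week 26 onward, apart from the nearly empty last windows.
- Deferred annual draws and liver work-up draws also enter.
- A repeat adds no second value in the same window, because one value per subject is used.
- EDC draws are not selected for high CK as such.
- The sampling rules are the same in both blinded arms, so a between-arm artefact needs symptom testing or discontinuation to differ by arm.
- No CK distribution, symptom rate or EDC rate is given, so a rise of a stated size would be assumption only.

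Three further points are fair. The SAP does not say in words that CK is plotted at all 15 visits; that follows from Table 4, and details are left to sponsor standards. The by-visit CK shifts are already limited to scheduled measurements. Safety summaries are descriptive, and no decision rule uses the plot.

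These points limit how far the concern goes but do not remove it. The reference to sponsor standards does not override the written rule that all observations fall in a window. EOS values do not make the points comparable either: for subjects on study drug the EOS visit is at least 14 days after the last dose, and which window an EOS value enters depends on the calendar date of entry.

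**Conclusion.** The concern holds in a limited form. Under the written rules, 11 of 15 windows (73%) have no scheduled annual CK. Means there combine symptom-triggered, repeat, liver work-up, deferred annual, EDC and EOS values, so mean CK change is not comparable across visits. Upward bias is plausible, chiefly at Weeks 4 to 14 and only if EOS came late enough after the last randomization that few EOS values fall there. That date is not in the documents.

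The window count rests on the documents alone. The shares of triggered values rest on the assumed rates and EOS timing, and on planned rather than actual accrual. The size of any bias is unknown. The tables designed to find individual CK elevations are unaffected. This is a should-fix matter of presentation in a descriptive safety output.

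**What to change.** In SAP 8.2.3, under clinical laboratory measurements:

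- Restrict the CK by-visit table of observed values and changes, and the longitudinal mean-change plot, to scheduled annual draws (Weeks 52, 104, 156 and 208). This matches the basis already used for the CK shift tables.
- Show EDC and EOS as separate rows or points, not joined to the time trend.
- Report n by arm at each point.
- State in one line whether a deferred annual draw counts as the annual draw it replaces.
- Leave the largest-post-baseline shift and the table of observations of potential clinical concern unchanged, so that every triggered value is still reported.

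The cost is a few lines of SAP text, a visit-type filter in one laboratory program, and fewer plotted points: 4 of the 15 windows remain, plus EDC and EOS. Data collection does not change.

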## **17. Depression**

If the subject's Patient Health Questionnaire (PHQ-9) score is  $\geq 15$  or there is a positive score in question 9 ([Section 7.3.2](#)), the subject should be excluded from participation, the subject's primary care physician (PCP) should be informed, and the subject should be referred to a mental health professional, either by the PCP or the investigator. Such subjects may be rescreened, at a later date, if they were evaluated and treated as appropriate, and the repeat PHQ scores permit inclusion. Any adverse events should be documented in the case report form as appropriate.

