The PHQ-2 consists of the first two items of the PHQ-9, and constitutes the two core DSM-IV items for major depressive disorder. The PHQ-2 score ranges from 0 to 6. The operating characteristics of this ultra-brief measure are quite good; the recommended cut-point when used as a screening test is a score of 3 or greater. This study will use a screening test score of 2 or greater, as a trigger for completion of the PHQ-9 assessment, as a more conservative approach to identifying the presence of a major depressive disorder. The PHQ-2 provides depressive scores and can be used as a screening assessment for depression; the remaining 7 questions of the PHQ-9 evaluate the severity of depression. The severity is calculated by assigning scores of 0, 1, 2, and 3, to the response categories of “not at all”, “several days”, “more than half the days”, and “nearly every day”, respectively. PHQ-9 total score ranges from 0 to 27. Scores of 1-4, 5-9, 10-14, 15-19, and 20-27 represent minimal, mild, moderate, moderately severe, and severe depression, respectively.

The PHQ-2 will be performed in all subjects at Visit 5 (randomization), and in subjects with cognitive assessments only, it will be performed annually, and at EDC or EOS.

Baseline value will be the last non-missing value on or before the day of randomization.

Adverse events

The Pfizer SAE Triage Group will identify potential disease-related efficacy endpoints (listed below) that are considered by the investigator to be causally related to study drug and report these into the Pfizer Drug Safety Unit (DSU):

- *Myocardial infarction, fatal or non-fatal.*
- *CV death.*
- *All cause death.*
- *Hospitalization for unstable angina needing urgent revascularization (PCI or CABG).*
- *Stroke, fatal or non-fatal.*
- *Hospitalization for unstable angina.*
- *Hospitalization for congestive heart failure.*
- *Arterial revascularization of any kind (eg, PCI, CABG, peripheral vascular surgery, carotid artery surgery).*

All adverse events occurring on or after the day of first informed consent will be included in reporting, regardless of whether or not the subject is on double-blind study medication. Adverse events during the screening period and adverse events with onset after the first dose of study medication will be summarized separately.

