7. HANDLING OF MISSING VALUES

For the clinical endpoints, not all subjects will have adjudicated and confirmed events. Subjects who do not experience any of the components of the primary endpoint will be censored on the date of last contact or 01November2016, whichever comes first. The date of last contact is defined as the date of death, if the date is not missing. Otherwise, the date of

last contact is defined as the study discontinuation date, the date of last visit, the date of last telephone contact, the onset date of the last AE, or the randomization date, whichever occurs last. The same censoring will be done for all other clinical endpoints and time to discontinuation from study. For analyses in the SAS, the date of first dose will be substituted for the randomization date.

Missing values for the Digit Span Forward, Digit Span Backward, Digit Symbol - Coding, Trail Making A and Trail Making B tests and the HVLT will not be imputed. For the Digit Span Forward and the Digit Span Backward, if the maximum number of digits is not reached and the last result is not a zero, the value will be missing.

Missing values for the PHQ-2 and PHQ-9 will not be imputed. If at least one item is missing, the total scores will be missing.

For all other efficacy and safety endpoints, missing values will not be imputed; missing values will remain missing.

For longitudinal analyses of circulating biomarker endpoints, a mixed model repeated measures (MMRM) model will be used for the analyses. As a likelihood method, MMRM models are valid when the data are missing at random (MAR). All subjects with a non-missing baseline value and at least one non-missing post-baseline value will be included in these analyses. Subjects with a missing baseline value will not contribute to the analyses. Consistent with MMRM model fitting, no explicit imputation of missing assessments will be performed.

Percent changes from baseline to last post-baseline value in LDL-C will be analyzed by analysis of covariance (ANCOVA). As a likelihood method, ANCOVA is valid when the data are MAR. Subjects with a non-missing baseline value and at least one non-missing post-baseline value will be included in the analyses. Subjects with a missing baseline value or without a non-missing post-baseline value will not contribute to the analyses.

When forming subgroups, subjects with a missing value on the classifying variable will not be included in a subgroup.

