The PHQ-2 score and PHQ-9 score will be summarized by treatment group at baseline as categorical variables according to sponsor standards using the following categories: scores of 0, 1-4, 5-9, 10-14, 15-19, and 20-27, which represent no depression, minimal, mild, moderate, moderately severe, and severe depression, respectively.

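### SAP 8.2.3 grades the 0-6 PHQ-2 with the 0-27 PHQ-9 severity bands, and its PHQ-9 table has a zero row that the planned procedures cannot fill and an unclear denominator

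*SAP*

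**What the plan says.** SAP 8.2.3, under Depression assessment, deals with both questionnaires in one sentence: "The PHQ-2 score and PHQ-9 score will be summarized by treatment group at baseline as categorical variables", "using the following categories: scores of 0, 1-4, 5-9, 10-14, 15-19, and 20-27". It labels the six categories, in order, no depression, minimal, mild, moderate, moderately severe and severe. Nothing limits the categories to the PHQ-9.

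SAP 6.2 describes the two scales separately. For the short form, "The PHQ-2 score ranges from 0 to 6". For the long form, "PHQ-9 total score ranges from 0 to 27", and the severity bands follow directly: "Scores of 1-4, 5-9, 10-14, 15-19, and 20-27 represent minimal, mild, moderate, moderately severe, and severe depression, respectively". The category for a score of 0 is not among those bands; SAP 8.2.3 adds it.

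SAP 6.2 also says that the PHQ-2 is the first two PHQ-9 items, that items score 0 to 3, and that the recommended screening cut-point is 3. It then sets a lower threshold: "This study will use a screening test score of 2 or greater, as a trigger for completion of the PHQ-9 assessment". Protocol 7.3.2 and SAP Appendix 2 (footnote 26) confirm that the other seven items are answered only after that trigger.

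SAP 7 rules out imputation for both scores and adds: "If at least one item is missing, the total scores will be missing". SAP 8.1.2 bases categorical percentages on subjects at risk in the treatment group, without saying who is at risk for a questionnaire given to only some subjects. Protocol 9.4 asks for a baseline summary of both scores by arm and names no categories, so the shared bands come from the SAP.

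**The concern.** A programmer who follows SAP 8.2.3 literally will put severity labels on the PHQ-2 that do not belong to it. Someone with the highest possible PHQ-2 would be listed as mild, and someone who screens positive by the recommended cut-point could be listed as minimal. The proportion screening positive, by either threshold the SAP mentions, could not be read from the PHQ-2 table.

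The PHQ-9 half has a different fault. It offers a row for no depression that nobody assessed as planned can enter, and it is silent on where subjects who screened negative are counted.

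What is at stake is modest but not nothing. The Protocol's document history for Amendment 1 says the assessment was added to capture baseline risk of depression, because depression may affect cognitive test performance. The baseline table is the only PHQ summary that the SAP plans.

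**Working it through.** **Reproducing the stated ranges.** With items scored 0 to 3, the PHQ-2 maximum is 2 × 3 = 6 and the PHQ-9 maximum is 9 × 3 = 27. Both agree with SAP 6.2.

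**PHQ-2 under the SAP 8.2.3 categories.**

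| PHQ-2 score | SAP label | Position against the SAP's own thresholds |
|---|---|---|
| 0 | no depression | below trigger |
| 1 | minimal | below trigger |
| 2 | minimal | meets trigger (2), below recommended cut-point (3) |
| 3-4 | minimal | meets trigger and recommended cut-point |
| 5-6 | mild | meets both; 6 is the maximum |

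The rows 10-14, 15-19 and 20-27 lie above 6, so three of the six rows are impossible. The 5-9 row can be reached only at 5 and 6. The largest difference hidden inside one row is 4 − 1 = 3 points, and that span crosses both thresholds.

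**PHQ-9 among those who complete it.** The PHQ-2 items are part of the PHQ-9, so the PHQ-9 total is at least the PHQ-2 score. With the trigger at 2:

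- smallest attainable total: 2 + 7 × 0 = 2
- largest attainable total: 6 + 7 × 3 = 27

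The 0 row therefore contains no attainable total, and the 1-4 row is in effect 2-4.

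**PHQ-9 among those who screen negative.** With a PHQ-2 of 0 or 1, seven items are never asked, so the SAP 7 rule makes the total missing. It cannot be read as 0. Had the items been asked, the total could have been anything from 0 + 0 = 0 to 1 + 7 × 3 = 22.

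**Upper rows.** Protocol 4.2, criterion 17, says that at a PHQ-9 of 15 or more, or a positive question 9, "the subject should be excluded from participation". Under that rule the attainable totals are 2 to 14. The Protocol's document history dates the depression assessment to Amendment 1 (01 October 2014) and this exclusion to Amendment 2 (12 February 2016). Rows 15-19 and 20-27 can therefore hold subjects randomized between the two.

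**Denominator.** Let p be the share of subjects with a PHQ-2 of 2 or more. A given PHQ-9 count is 1/p times as large a percentage of completers as of all subjects with a PHQ-2, if every triggered PHQ-9 is complete. The documents give no value for p. Purely as an assumption, p = 10% gives a factor of 1/0.10 = 10 and p = 30% gives 1/0.30 ≈ 3.3. SAP 8.1.2 does not settle which denominator applies.

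**The case against.** The strongest reply is that this is a drafting slip of little consequence. The sponsor may have meant the bands for the PHQ-9 alone, an empty row misleads nobody, and no PHQ term enters the primary, key secondary or cognitive models in SAP 8.2.1 to 8.2.3. The point about consequence stands. The point about intent does not remove the problem, because SAP 8.2.3 names both scores and gives one set of categories.

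Three stronger readings might be inferred, and the documents do not support them.

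- *That the PHQ-9 table overstates depression.* This holds only with a completers-only denominator. If subjects at risk in SAP 8.1.2 means everyone in the arm, the percentages are not inflated by conditioning on a positive screen; the rows simply fail to add to 100%.
- *That rows 15-19 and 20-27 contain only subjects who should have been excluded.* The exclusion came with Amendment 2, after the questionnaire was in use, so earlier subjects can be there legitimately.
- *That the tables cannot show whether the arms were balanced.* Both are by arm and at baseline, and the trigger acts before randomized treatment, so comparing completers between arms is not biased by it. The PHQ-2 table still separates 0, 1-4 and 5-6, and the PHQ-9 row counts sum to the screen-positive subjects with a complete PHQ-9. The comparison is coarse, but possible.

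**Conclusion.** The point holds as a fault in a stated rule, with low consequence. On the PHQ-2, three of six rows are impossible, the maximum is called mild, and one row merges a negative screen with scores on both sides of the recommended cut-point. On the PHQ-9, the no-depression row is empty by construction, subjects who screen negative have no value, and the denominator is unclear.

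The empty row assumes that procedures are followed: a PHQ-9 completed in error after a PHQ-2 below 2 could produce a 0. None of the conclusions depends on the assumed 10% to 30% screen-positive share, which only illustrates how much the choice of denominator could matter. The effect stops at a descriptive baseline table; alpha, power and all model-based analyses are untouched.

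**What to change.** In SAP 8.2.3, separate the two scores.

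- **PHQ-2:** show number and percent at each score from 0 to 6, plus the proportions at 2 or more and at 3 or more, by arm, without PHQ-9 severity labels.
- **PHQ-9:** keep the severity bands for this score only. Replace the zero row with one for PHQ-9 not administered because the PHQ-2 was below 2. Add a line for a triggered but incomplete PHQ-9, so that the rows add up.
- **Denominator:** state it as all subjects with a baseline PHQ-2.

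Repeating the tables for the cognitive-testing subset (about 500 subjects) would serve the stated reason for collecting the data, but it is optional.

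The cost is a few lines of SAP text and a revised table shell. All the data are already planned for collection, and no other analysis is affected.
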